## Definitions:

Clinical cure is a positive answer to the question “Is the child cured?” or if not cured “Has the child improved?” asked to caregiver through a phone call at day 7. Non-referred secondary hospitalizations (see definition below) will be considered as clinical failures even if the child is already cured at day 7.

Clinical failure is a negative answer to the question “Is the child cured?” and “Has the child improved” asked to the caregiver through a phone call at day 7. Non-referred secondary hospitalization (see definition below) will be considered as a clinical failure even if the child is already cured at day 7.

Initial consultation is the first visit of a sick child for an acute problem at a HF participating in the study (and thus registered electronically); timeframe from completion of the initial visit up to midnight of the same day. The initial consultation is considered as day 0.

Re-attendance visit is a consultation (not necessarily at a HF participating in the study) taking place from the day after initial consultation up to day 14 included. A re-attendance visit can be scheduled (proposed by the health care worker on a certain day) or unscheduled (upon decision by caregivers).

Primary referral is a decision of referring or admitting the child at a hospital or health center for at least one night, taken by the health care worker at the initial consultation.

Secondary referral is a decision of referring or admitting the child at a hospital or health center taken by the health care worker during a re-attendance visit taking place from the day after initial consultation up to day 7 included.

Primary hospitalization is an admission to a hospital or health center ward for at least one night taking place the same day as the initial consultation

Secondary hospitalization is an admission to a hospital or health center ward for at least one night taking place from the day after initial consultation up to the phone call at day 7 included. A non-referred secondary hospitalization is a direct visit to hospital without a re-attendance visit the same day at a HF participating in the study. Non-referred secondary hospitalization will be determined if the caregiver reports during the day 7 phone follow-up that the child was hospitalized, but there was no documentation of a referral from initial and re-attendance visits at participating health facilities.

Antibiotic prescription is any oral, intramuscular or intravenous (but not topical) antibiotic prescribed by a HCW during the initial consultation or a re-attendance visit.

Antimalarial prescription is any oral, rectal, intramuscular or intravenous antimalarial prescribed by a HCW during the initial consultation or a re-attendance visit.

Febrile child is a child with a history of fever (measured or suspected fever in the past 48 hours) or a high temperature.

Malaria testing is a malaria RDT or microscopy ordered by a HCW during an outpatient visit.

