- Primary referral is a decision of referring the child to hospital taken by the HCW at the initial consultation
 Secondary referral is a decision of referring the child to hospital taken by the HCW during a re-
- attendance visit taking place from the day after initial consultation up to day 7 included.
- Primary hospitalization is an admission to a hospital ward taking place the same day as the initial consultation
- Secondary hospitalization is an admission to a hospital ward taking place from the day after initial consultation up to the phone call at day 7 included. A non-referred secondary hospitalization is a direct visit to hospital without a re-attendance visit the same day at a HF participating in the study.
- Antibiotic prescription is any oral, intramuscular or intravenous (but not topical) antibiotic prescribed by a HCW during the initial consultation or a re-attendance visit
- Antimalarial prescription is any oral, rectal, intramuscular or intravenous antimalarial prescribed by a HCW during the initial consultation or a re-attendance visit
- Febrile child is a child with a history of fever and/or a high temperature
- Malaria testing is a malaria RDT or microscopy ordered by a HCW during an outpatient visit
- Day 7 is a range of 6-14 days post initial consultation to allow for completion of home visit for children whose caregiver reports having no phone / no phone number.

Additional longitudinal analyses:

- Change in % of children prescribed an antibiotic over time

- Change in % of children with basic anthropometrics and clinical signs measured over time (intervention arm only)
- Change in % of consultations where ePOCT+ was used over time (intervention arm only)

7.2 Indicators for Objective 2: Improve the algorithm and adapt it to spatiotemporal variations

- Number of positive impact modifications in the algorithm identified by ML-based analyses
- Number of positive impact modifications tested through randomized sub-studies
- % of these positive impact modifications confirmed to be safe and useful by randomized sub-studies
- Number of modifications implemented by type of impact (better clinical cure, less severe clinical outcomes, less medicines or diagnostic tests needed, shorter consultation time...)

Definitions used for the indicators of objective 2

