8.1.7 Measurement of primary and secondary outcomes

Data captured on the tablets used by health care workers during the consultation

During the pilot phase before Phase 1 begins, tablets will be provided to HCWs in both intervention and control HFs. In intervention HFs the tablets will contain the patient registration module followed

by the ePOCT+ algorithm that will guide them throughout the consultation process. In control HFs, tablets will only collect the patient demographics (see **Appendix 1**).

To determine the percentage of children prescribed an antibiotic or an antimalarial, as well as to know the final decision on referral and final diagnoses retained by HCWs, four questions will appear on the screen at the end of the consultation process, i.e. once the clinician has gone through the entire algorithm in intervention HFs or just after the patient registration module in control HFs. HCWs will be asked to document the final decision regarding the need for referral, tests performed and the results, decision on the date of follow-up (if needed), final diagnoses and final treatments prescribed. For each medicine prescribed, the dosage and duration of the treatment will also be recorded (see **Appendix 1**).

Data captured through phone calls or home visits (Phase 1) or automated phone calls or SMS (Phase 2) to caregivers

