## 5.4 Baseline characteristics

The baseline cluster (health facility) characteristics that will be summarized by study arm include:

- Number of health facilities by type (dispensary or health center) and region
- Average number of patients seen per month by health facility type
- Availability and readiness of basic health care services score based on the Tanzanian Service Provision Assessment (median and IQR)

The baseline patient characteristics that will be summarized by study arm, and for the overall study include:

- Demographics: sex (number and percentage); age (median and IQR), age groups 0-2 months, 2 months - 5 years, 5-14 years (number and percentage)
- Medical history: Main reasons for consultation, history of fever (number and percentage)

Given the pragmatic nature of the study, and so as not to influence the normal management of patients and their outcome in the control arm, clinical signs and comorbidities will not be systematically collected in the control and intervention arm.

No formal statistical comparisons of baseline data will be performed.

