#### 6.1.2 Secondary outcomes

All secondary outcomes are compared between the intervention (ePOCT+) and control (routine care) arms.

*1) Secondary consultations*

- % of children with one or more unscheduled re-attendance visits at any health facility by day 7

Timing and method of measurement: Telephone or home visit follow-up 7 days (range 6-14 days) after enrollment of the subject. The day of enrollment of the subject is considered as day 0.

*2) Severe outcome by day 7*

- % of children with non-referred secondary hospitalization by day 7
- % of children who have died by day 7

Timing and method of measurement: Death and non-referred secondary hospitalization will be assessed by telephone or home visit follow-up 7 days (range 6-14 days) after enrollment of the subject. The day of enrollment of the subject is considered as day 0.

*3) Primary referrals*

- % of children referred to hospital or inpatient ward at a health centre at initial consultation

Timing and method of measurement: Documented by the health care worker at the end of the initial consultation in the eCRF (control arm) or in ePOCT+ (intervention arm) when the subject was enrolled (day 0)

*4) Appropriate case management for malaria at initial consultation*

- % of febrile children tested for malaria by RDT and/or microscopy at day 0
- % of malaria positive children (positive RDT result OR positive microscopy result) prescribed an antimalarial at day 0
- % of malaria negative children prescribed an antimalarial at day 0
- % of untested children prescribed an antimalarial at day 0

Timing and method of measurement: Documented by the health care worker at the end of the initial consultation where the subject was enrolled (day 0)

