Effect modification of the co-primary outcomes of antibiotic prescription and clinical failure will be performed in groups of patients where the highest reduction in antibiotic prescription is expected, and areas of extension of the content of the algorithm compared to the version tested in the previous ePOCT study. Effect modification by sex, age group (young infants ages 1 to 59 days, children aged 2 months to 5 years, and children aged 5 to 14 years), respiratory symptoms, fever without clinical source, gastrointestinal complaints (vomiting and diarrhea), skin problems, ear, nose and throat problems, will be assessed by incorporating an interaction between arm and the respective variable, acknowledging that power will be low. All models will be adjusted for clustering and the stratification factors (Kahan & Morris, 2012). Furthermore in order to adjust for potential imbalances in baseline characteristics between study groups, relevant baseline characteristics will be included as fixed effect variables in the final model. Baseline characteristic imbalance will be determined by consensus among the study analysis team.

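### The percentage of febrile children tested for malaria uses a denominator that, as documented, is probably ascertained differently in the two arms

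*SAP*

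**What the plan says.** The SAP's definitions read: "Febrile child is a child with a history of fever (measured or suspected fever in the past 48 hours) or a high temperature". The protocol's definitions in section 7.1 have the same two parts: a febrile child "is a child with a history of fever and/or a high temperature". Neither gives a temperature cut-off or says where the temperature comes from.

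SAP 6.1.2 compares all secondary outcomes between arms. One of its four malaria outcomes is the percentage "of febrile children tested for malaria by RDT and/or microscopy at day 0". The others use different denominators: the percentage "of malaria positive children (positive RDT result OR positive microscopy result) prescribed an antimalarial at day 0", the percentage "of malaria negative children prescribed an antimalarial at day 0", and the percentage of untested children given an antimalarial.

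On data capture, SAP 6.3 plans an analysis of how often temperature and other basic measurements are documented inside ePOCT+, for the intervention arm only. For the control arm, Protocol 8.1.7 says "In control HFs, tablets will only collect the patient demographics", followed by end-of-consultation questions on referral, tests and results, follow-up date, diagnoses and treatments. SAP 3.1 calls the control instrument a simple eCRF. SAP 5.4 explains that, so as not to alter control-arm care, "clinical signs and comorbidities will not be systematically collected in the control and intervention arm". It also lists history of fever as a baseline item summarised by arm.

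SAP 6.2 names "fever without clinical source" as an effect modifier for both co-primary outcomes.

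**The concern.** A between-arm percentage is interpretable only if children enter the denominator by the same route in both arms. Here one of the two routes needs a recorded temperature, and the plan describes that record for the ePOCT+ arm only. A control child with an unrecorded high temperature and no reported fever would leave the outcome altogether, whether tested or not. A similar child in an ePOCT+ facility would be counted. Part of any difference in malaria testing could then reflect who was classed as febrile rather than how febrile children were managed.

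The fever subgroup raises a related but separate question. Whether a fever has a source can depend on the examination, and Protocol 6.1 says that ePOCT+ guides the examination. If the subgroup is built from examination findings, allocation can change membership.

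**Working it through.** No sample size, power or error rate in the plan depends on this point, so there is no stated figure to reproduce. The check compares the sources and then asks how large the effect could be.

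**Step 1: what each arm is documented to record**

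| Item | ePOCT+ arm | Control arm |
|---|---|---|
| History of fever | Yes, baseline item by arm (SAP 5.4) | Yes, same item (SAP 5.4) |
| Temperature | Documented within ePOCT+ (SAP 6.3) | Not among the listed items (Protocol 8.1.7, SAP 3.1) |
| Malaria test and result | Yes | Yes |

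The arms therefore share the children with a history of fever. They differ only in those with a high temperature and no reported history.

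**Step 2: the size of the distortion**

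Let q be the share of the ePOCT+ febrile denominator identified by temperature alone, h the testing rate in children with a history of fever, and t the rate in temperature-only children. Suppose that testing behaviour is the same in both arms and that the control denominator holds only children with a history of fever.

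- ePOCT+ percentage: (1 − q)h + qt
- Control percentage: h
- Difference due to the definition alone: q(t − h)

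Example: with q = 0.05, h = 0.80 and t = 0.60, the ePOCT+ percentage is 0.95 × 0.80 + 0.05 × 0.60 = 0.79. The control percentage is 0.80, so the artefact is −1.0 point.

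The documents give none of q, h or t. All the values below are assumptions; the entries are percentage points.

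| q | h 0.80, t 0.40 | h 0.80, t 0.60 | h 0.80, t 0.80 | h 0.80, t 0.95 | h 0.60, t 0.95 |
|---|---|---|---|---|---|
| 2% | −0.8 | −0.4 | 0 | +0.3 | +0.7 |
| 5% | −2.0 | −1.0 | 0 | +0.75 | +1.75 |
| 10% | −4.0 | −2.0 | 0 | +1.5 | +3.5 |
| 15% | −6.0 | −3.0 | 0 | +2.25 | +5.25 |

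**Step 3: the same calculation from the control side**

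If the intended group is all febrile children, including those found by thermometer, the ePOCT+ figure is right and the control figure is incomplete. It reports h instead of (1 − q)h + qt, with q, h and t now being control-arm values. The error in the contrast is again q(t − h).

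**Step 4: after the change**

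With history of fever as the only criterion in both arms, q = 0 and the definitional difference is 0 by construction.

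**The case against.** The strongest reply is that the gap in the control arm is inferred. The control case report form is in Appendix 1, which is not part of the text available for this review. Protocol 8.1.7's phrase about demographics cannot be taken literally, since the same section goes on to list tests, diagnoses and treatments. The synopsis says that the control application records the data needed for outcomes, and febrile status is such data. Protocol 8.1.2 describes temperature at triage before it separates the arms, and does not limit the triage module to one of them. SAP 5.4's sentence on clinical signs names both arms. All of this stands, and it is why the finding is worded as probable. It does not supply what is missing: a statement of how a high temperature is ascertained in control facilities. Occasional recording by control staff would still be selective.

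A second reply is that the shift may be close to zero. Protocol Table 2 directs malaria rapid tests at patients with fever, and Protocol 8.2 says that the standard fever branch recommends testing them all, so t may be close to h in the ePOCT+ arm. That is fair, although Protocol 8.1.6 allows providers to override the tool. It also answers only the ePOCT+ side. In routine care the two rates could differ.

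A third is that observers in the quality-of-care surveys record vital signs and tests requested in facilities of both arms (Protocol 3.4.1 and 8.1.7). This offers a cross-check in 18 of the 40 facilities, but SAP 6.1.2 takes the outcome from health-worker records.

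On the subgroup, neither document says how fever without a source will be derived, so derivation from the examination is a possibility and not a stated plan. SAP 6.2 already concedes low power for these interactions.

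**Conclusion.** The point holds for one secondary outcome. As documented, the percentage of febrile children tested for malaria has a denominator that is probably ascertained differently by arm, and the plan has no provision to prevent this. The conclusion rests on the control form having no equivalent temperature field, which the text suggests but does not state.

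The size and sign of the bias cannot be derived from the documents. Over the assumed range it runs from about −6 to +5 points, and from −2 to about +2 points at q = 5%. It is zero if temperature-only children are tested as often as those with reported fever.

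A reader might infer that all the malaria results compare different populations. They do not: the other three use test-positive, test-negative and untested children, and even for this outcome the arms share the fever-history group. A reader might also infer that the trial's main conclusion is affected. The success criterion in SAP 6.2 rests on clinical failure and antibiotic prescription, and neither uses this denominator. Nor do the documents establish that the fever interaction is invalid; they leave its definition open, which is a secondary matter worth closing.

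**What to change.** For this outcome, define febrile in both arms as caregiver-reported history of fever in the past 48 hours, asked identically in both arms, and state that a temperature taken at the presenting visit does not count. That exclusion is needed because the SAP's current wording counts measured fever as history, which could let the presenting temperature back in. Keep the temperature-inclusive percentage as a description of the ePOCT+ arm only, with the cut-off that was used stated.

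As a secondary change, build the fever effect-modification group from fever history and reasons for consultation. SAP 5.4 plans both as baseline items by arm, and neither need depend on a source found at examination.

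The cost is SAP wording and a check that the fever question is the same in both instruments; no new data item is planned. The downside is small: children whose fever is found only by thermometer leave the denominator, so the outcome describes testing among children with reported fever.

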Analysis: Compare change in percentage of prescription from month to month, and from first half of the study compared to second half of the study for the intervention arm and the control arm, using the control arm as comparison to correct for seasonality, and presenting implementation team mentorship visits and combined implementation team and CHMT mentorship visits to contextualize changes. Independent sample t-test will be used to compare change in antibiotic prescription between intervention and control arm.

- Change in % of children with basic anthropometrics and clinical signs assessed (intervention arm only)

Timing and method of measurement: Measurement and documentation of individual basic measurements (height, MUAC, Temperature), and clinical signs (respiratory rate) as documented within the ePOCT+ tool during the initial assessment (Day 0).

Analysis: Descriptive statistics presenting change in documentation of basic measurements and clinical signs from month to month, and from first half of the study compared to second half of the study. Dates of implementation team mentorship visits and combined/supervised implementation team and CHMT mentorship visits and any changes in implementation strategy will also be presented to contextualize the changes. Subgroup analyses may be conducted for each intervention health facility.

- Change in % of cases managed using ePOCT+ over time (intervention arm only):

Timing and method of measurement: Uptake of ePOCT+ is defined as the use of the ePOCT+ tool to guide the clinical consultation including the decision on what treatment to prescribe during the initial consultation (Day 0).

Analysis: Descriptive statistics to present change in the proportion of health care workers' uptake from month to month, and from first half of the study compared to second half of the study will be presented. Dates of implementation team mentorship visits and combined/supervised implementation team and CHMT mentorship visits and any changes in implementation strategy will also be presented to contextualize the changes. Subgroup analyses may be conducted for each intervention health facility.

- Prognostic value of individual or combined predictors during the initial consultation to predict clinical failure/cure, hospitalization for more than one night and mortality (intervention arm)

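### The febrile-child denominator of the malaria-testing outcome can be entered through a measured temperature, for which the documents describe a source in ePOCT+ but none in the control eCRF

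*SAP*

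**What the plan says.** SAP section 6.1.2 lists among its malaria outcomes the percentage "of febrile children tested for malaria by RDT and/or microscopy at day 0", and states: "All secondary outcomes are compared between the intervention (ePOCT+) and control (routine care) arms". The definitions that follow give two routes into the denominator: "Febrile child is a child with a history of fever (measured or suspected fever in the past 48 hours) or a high temperature". Protocol section 7.1 has the same two routes: a febrile child "is a child with a history of fever and/or a high temperature". Neither document gives a temperature threshold, a data source by arm, or a rule for a child with no recorded temperature.

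On data capture, SAP section 6.3 describes "Measurement and documentation of individual basic measurements (height, MUAC, Temperature), and clinical signs (respiratory rate) as documented within the ePOCT+ tool". That analysis is confined to the intervention arm, as is its counterpart in Protocol section 7.1. For the control arm, Protocol section 8.1.7 says: "In control HFs, tablets will only collect the patient demographics". Questions at the end of the consultation follow, covering referral, tests, follow-up, diagnoses and treatment. SAP section 3.1 calls the control tool a simple eCRF with no decision support. SAP section 5.4 adds that "clinical signs and comorbidities will not be systematically collected in the control and intervention arm", with the aim of leaving normal management undisturbed. The only fever item it lists for summary by arm is history of fever.

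**The concern.** A denominator built on an either/or rule is comparable between arms only if both routes are ascertained alike. Here the intervention tool is itself the described source of one route. Take a child with no reported fever who is found hot on examination. In an intervention facility the reading is documented in ePOCT+ and the child counts as febrile. In a control facility the documents describe no field through which that reading would reach the dataset.

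Randomising facilities does not protect against this, because ascertainment happens after allocation and depends on the tool. The planned logistic model cannot repair it either: control children febrile by measurement only would not be identifiable. SAP section 6.3 also examines how documentation of temperature changes over the study, so the intervention denominator could move with documentation habits while the control denominator does not. The result at stake is one component of one secondary outcome. The other three malaria components, on antimalarial prescribing, do not use the febrile definition.

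**Working it through.** The plan states no figure for this outcome, so there is none to reproduce. The check sets the rule against the described data sources, then illustrates the possible size.

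**Step 1. Source of each route, by arm**

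| Route into the denominator | Intervention | Control |
|---|---|---|
| History of fever | Listed for summary by arm (SAP 5.4) | Listed for summary by arm (SAP 5.4) |
| High temperature | Documented within ePOCT+ (SAP 6.3) | No source described (Protocol 8.1.7, SAP 3.1) |

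Protocol section 8.1.2 also has temperature measured at triage, using the ePOCT+ triage module, without naming the arm.

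**Step 2. Formula**

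Suppose testing of children with a fever history is equal in the two arms. Let

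- t_h = proportion tested among children with a fever history (same in both arms);
- t_x = proportion tested among temperature-only febrile children in the intervention arm;
- x = number of temperature-only children divided by number with a fever history.

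If no temperature-only child enters the control denominator, the control percentage is t_h and the intervention percentage is (t_h + x·t_x)/(1 + x). The artefact is the difference:

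shift = x(t_x − t_h)/(1 + x)

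**Step 3. Assumed inputs**

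The documents give none of these quantities. The assumed ranges are x from 1% to 10%, t_h from 60% to 95%, and t_x from 20% to 98%.

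**Step 4. Results, in percentage points**

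| t_h | t_x | x = 1% | x = 5% | x = 10% |
|---|---|---|---|---|
| 95% | 20% | −0.74 | −3.57 | −6.82 |
| 80% | 50% | −0.30 | −1.43 | −2.73 |
| 80% | 80% | 0.00 | 0.00 | 0.00 |
| 60% | 98% | +0.38 | +1.81 | +3.45 |

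Worked example: t_h = 0.80, t_x = 0.50, x = 0.05 gives 0.05 × (−0.30)/1.05 = −0.0143, or −1.43 points. The first and last rows are the extremes of the assumed ranges.

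**Step 5. Reading the results**

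The sign depends only on whether temperature-only children are tested more or less often than those with a fever history. Protocol Table 2 directs the malaria rapid test at patients with fever, which could raise t_x. Protocol section 8.1.6 lets health workers override the tool, which could lower it. The direction cannot be called conservative in advance. The table shows the full-gap case: temperatures recorded in control facilities, or missing in intervention facilities, would shrink every entry.

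**The case against.** The strongest reply is that a gap in the control form is being inferred without the form. Protocol Appendix 1, which holds the case report forms, is not among the documents, and several passages weaken the inference.

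- Protocol section 8.1.7 cannot be an exhaustive list. Read literally, demographics plus the closing questions would also exclude history of fever and reason for consultation, yet SAP section 5.4 summarises both by arm.
- The protocol synopsis says the control application records data related to the outcome measures. Febrile status is part of an outcome, so a temperature field would fit.
- SAP section 5.4 speaks of both arms, and not systematic is weaker than never. SAP section 6.3 groups temperature with basic measurements, apart from clinical signs, so the statement in 5.4 may not cover it.
- Triage temperature in Protocol section 8.1.2 is not limited to one arm. The ePOCT+ label does not settle it, because section 8.1.3 says the ePOCT+ registration module is used at every participating facility.
- The SAP's history of fever includes measured fever in the past 48 hours. A child hot at the visit might be entered under history in either arm.

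All five stand as limits on certainty. A reader might infer that the control eCRF records no temperature, that a temperature-only control child can never count, or that the plan applies different rules to the arms. The documents do not support this. The written rule is the same for both arms, the form is unseen, and the history item may already admit some of these children.

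None of the five gives the control arm a described source for temperature, and the last shows that the history item needs tightening too. The point therefore goes beyond a request for missing detail: applying the rule to the sources that the plan describes gives ascertainment that depends on arm.

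**Conclusion.** The concern holds as a weakness in one pre-specified secondary comparison. As the tools are described, children febrile by measurement only can enter the denominator more readily in the intervention arm, so a difference in malaria testing may partly reflect data capture.

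Its size and direction are unknown. The illustration stays under 1 point in every case at x = 1% and reaches a few points at x = 10%, with either sign. It does not establish a material bias. It rests on assumed testing rates, an assumed share of temperature-only fever, equal testing of children with a fever history, and no control-arm capture of temperature. The co-primary outcomes, the sample size and the success criterion are unaffected. The definition should be changed, but the point does not threaten the trial's main conclusions.

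**What to change.** For the between-arm outcome, define febrile as caregiver-reported history of fever in the past 48 hours, recorded by the same item in both arms and not filled from the temperature measured at the visit. The last condition matters because the SAP's present wording counts measured fever as history, so a denominator based on history alone could still absorb extra readings from ePOCT+. Align the definition in Protocol section 7.1 so that the two documents agree, and make both changes before results by arm are seen.

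Report the temperature-inclusive definition only as an intervention-arm description. If the control eCRF turns out to capture temperature, it can instead be a between-arm sensitivity analysis, with the source in each arm, the threshold and the handling of missing readings stated.

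No new data should be needed, since SAP section 5.4 already lists history of fever by arm; the item wording should be checked against the two forms. The cost is a short SAP revision and a matching protocol amendment. A small group of temperature-only febrile children leaves the denominator, the pre-specified definition is narrowed, and any gain from testing those children would show only in the intervention-arm description.
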